status will be assessed by determining changes in serum concentrations of retinol, ferritin, transferrin receptor (TfR) and hemoglobin before and after intervention in the treatment and control groups. These markers will be the outcome measures of any change in vitamin A and iron status in the children. A mid-point blood analysis at 3 months will also be done to measure of the onset of a detectable change.

Concerned agencies may use the results of this study for planning food fortification program in Bangladesh as well as in other developing countries. It may also stimulate local food companies to come forward with new strategies in areas of fortification and take an effective role in micronutrient intervention programs. Similarly, the Government of Bangladesh may use this information to formulate policies regarding food fortification.

KEY PERSONNEL (List names of all investigators including PI and their respective specialties)

Name	Professional Discipline/ Specialty	Role in the Project
1. I. [name]	Senior Operations Researcher / Nutrition	PI
2. [name]	Director, ICDDR,B	Co-PI
3. [name]	Senior Operations Researcher / Public Health Research	Co-PI
4. [name]	Operations researcher / Public Health research	Co-Investigator
5. [name]	Associate scientist / Biochemistry Lab	Co-Investigator
6. [name]	Scientist / Clinical nutrition	Co-Investigator
7. [name]	Field Operations Manager	Co-Investigator
8. [name]	Associate Scientist / Paediatric Nutrition	Co-Investigator

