### Specific Aims:

Describe the specific aims of the proposed study. State the specific parameters, biological functions/ rates/ processes that will be assessed by specific methods (TYPE WITHIN LIMITS).

The aim of the study is to evaluate whether an impact of consuming *chapatti* made from vitamin A and iron fortified wheat flour by the school aged children can be demonstrated

1. Primarily, on their vitamin A status reflected in serum retinol concentration at 6 months
2. Secondly, on iron status reflected in serum ferritin, TfR and hemoglobin concentration at 6 months

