The study had a one-month pretest to establish procedures and preparation of the field settings including handling, storage of wheat flour, making of *chapattis* and see chapatti consumption pattern. Our pretest reveal that two chapattis made from 100g flour were consumed by all the 43 participants except one and well accepted when served with a condiment (halwa made of suji and sugar). This will be followed by a six month period when participant children will consume two chapattis (100 g flour) daily in addition to their usual food.

An organoleptic analysis of chapatti made from fortified flour was performed by Institute of Nutrition and Food Science, Dhaka University (INFS,DU) with a group of penalists experienced in organoleptic tests except one (21). The analyses based on hedonic scales of different parameters, reveal that chapatti made from fortified atta (flour) using hot water has a number of qualities with high acceptability.

The sampling unit will be the bari (composed of an average of five households and a population of about 30 per bari). The selected baris will be randomized to receive in a blinded manner either fortified or unfortified wheat flour and also receive a condiment (i.e., dal, suji, sugar etc.) to increase consumption compliance. Before feeding starts, measures like z-scores for weight-for-age, weight-for-height, height-for-age, blood hemoglobin, serum retinol, serum ferritin and serum transferrin receptor will be taken to see baseline comparability. The outcome measures that are expected to change in the group receiving fortified *chapatti* are serum retinol, serum ferritin and serum transferrin receptor concentrations. Also a change in hemoglobin level is expected. Each of these measures (weight, height, Hb level, serum retinol, serum ferritin, serum transferrin receptor) will be determined at the start (0 month), at the mid-point (3 months) and at the end of the trial (6 months).

Table: Level of fortificants per kg wheat flour and contribution from *chapatti* consumption (100g flour) to micronutrient requirements of children

Nutrient	Level in flour	Contribution of flour to requirements of children 6-15 years old		
		Nutrient consumed (per day)	RDA	% RDA
Vitamin A 	10,000 IU/kg	212 µg 	400 - 600 µg	53 - 35%
Iron 	66.0 mg	3.3 mg 	10 - 15 mg	33 - 22%
Thiamin (Vit. B 1 )	6.4 mg	0.64 mg	1.2 mg	53%
Riboflavin (Vit. B 2 )	4.0 mg	0.40 mg	1.0 mg	40%

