#### SAMPLE SIZE ESTIMATION:

Sample size was estimated by taken into account the *mean and standard deviation (SD) of serum retinol concentrations*. Unfortunately, there are no data on serum retinol or serum ferritin distributions in this age group in rural Bangladesh on which to base a sample size. However, in a trial in Guatemala [Arroyave et al. 1981] (22), the mean  $\pm$  SD of serum retinol concentrations were  $29.2 \pm 10.2$   $\mu\text{g/dL}$  and  $34.2 \pm 9.5$   $\mu\text{g/dL}$  before and after 1 year of supplementation with sugar fortified with vitamin A. With this level of change, we require 83 subjects in each group (5% significance level and a power of 90%).

Sample size was also estimated by taken into account the *mean and standard deviation (SD) of serum ferritin concentrations*. In a trial in Venezuela [Layrisse et al. 1996] (14), the mean  $\pm$  SD of serum ferritin concentrations were  $18.01 \pm 13.8$   $\mu\text{g/L}$  and  $25.2 \pm 15.3$   $\mu\text{g/L}$  before and after supplementation with maize and wheat flour fortified with iron. With this level of change, we require 87 subjects in each group (power of 90% and 5% level of significance).

Considering the greater of the two estimates (87 subjects), the calculated sample size has been doubled to 175 in each group to account for cluster and dropout effects. With a population of 30 in each bari in the study area and 4 eligible children (6-15 years) in each bari we require 44 baris in the experimental and 44 baris in the control group.

Sample size estimation was done by using the formula:

$$\frac{2(\text{SD})^2 \times \text{factor for } \alpha, \beta}{(\text{WD})^2}$$

Where, SD is the standard deviation and WD is the worthwhile difference between the means.

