## Data Analysis

Describe plans for data analysis. Indicate whether data will be analyzed by the investigators themselves or by other professionals. Specify what statistical softwares packages will be used and if the study is blinded, when the code will be opened. For clinical trials, indicate if interim data analysis will be required to monitor further progress of the study. (TYPE WITHIN THE PROVIDED SPACE).

The groups will be compared to ensure the comparability of the groups at the start of the study. The comparisons will include z-scores of weight-for-age (WA), height-for-age (HA) and weight-for-height (WH), hemoglobin, serum retinol, serum ferritin and serum TfR. These should be statistically similar at the start of the study. However, randomization design of the study is also expected to take care of comparability between the two groups. The same data points will be compared after three and six months of consuming *chapattis*. Within six months, it is expected that serum retinol will be significantly increased in the fortified group compared to the unfortified group. We expect that the TfR will be decreased within six months since there will be fewer binding sites available.

Outcome measures including retinol, ferritin and TfR will be compared both within and between groups from start to the end of the trial. Change in nutritional status reflected by z-scores for WA, WH and HA, although not outcome measures, will also be investigated. Means of continuous variables, if normally distributed, will be compared by Student's t test. If the data of continuous variables do not conform to a Gaussian distribution, non-parametric tests including Mann-Whitney test will be used. Difference in categorical variables will be assessed by chi-square test. The confounding will be controlled by multiple regression analyses. An analysis of covariance will be performed for comparing the final levels of the outcome variables making allowances for any difference between the initial or 3-month levels.

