## Ethical Assurance for Protection of Human Rights

Describe in the space provided the justifications for conducting this research in human subjects. If the study needs observations on sick individuals, provide sufficient reasons for using them. Indicate how subject's rights are protected and if there is any benefit or risk to each subject of the study.

Fortification of food has been found to be an effective way of improving micronutrient status of people. Although micronutrient deficiency is very common in Bangladesh, fortification of food with iron, vitamin A and other micronutrients has not been tested in this country. There is, therefore, a logical need to do research in children in Bangladesh.

Participation is purely on a voluntary basis. Consent will be obtained in written from the parents/guardians and participants who are 8 years older or above. Rights of subjects are protected as they can withdraw from the study at any point.

The study does not involve any potential risk to the participating children. In addition to taking weight and height measurements, samples of blood (5 mL) will be collected from study subjects three times during the whole study period with utmost aseptic condition. Apart from known complications of blood drawing i.e., temporary discomfort/pain or rare instances of bruising at the site of puncture etc., participation poses no substantial risk to the study subjects. Well-experienced personnel will perform all the sampling procedures.

[name]

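### The named 6-month comparisons use only children with a 6-month sample although dropout is expected; one model of the 3- and 6-month values would be slightly more precise and more robust

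*Protocol*

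**What the plan says.** The Specific Aims put one outcome first: "Primarily, on their vitamin A status reflected in serum retinol concentration at 6 months". Blood is drawn at 0, 3 and 6 months.

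The 3-month sample has its own stated purposes. The Project Summary says: "A mid-point blood analysis at 3 months will also be done to measure of the onset of a detectable change". The Data Analysis section plans a group comparison at that visit: "The same data points will be compared after three and six months of consuming".

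For the comparison itself, Data Analysis says "Means of continuous variables, if normally distributed, will be compared by Student's t test", with Mann-Whitney as the fallback. It adds: "An analysis of covariance will be performed for comparing the final levels of the outcome variables". The sentence goes on to allow adjustment for either the starting value or the 3-month value.

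Dropout is expected. Under Sample Size Estimation the calculated number is "doubled to 175 in each group to account for cluster and dropout effects", with no separate rate for either. The Ethical Assurance section says of the children that "they can withdraw from the study at any point".

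**The concern.** A t test, a Mann-Whitney test and an ANCOVA of the final level all need a 6-month value. A child with baseline and 3-month retinol but no 6-month draw falls out of the primary comparison, although the 3-month value carries information about the missing one.

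Two things are at stake. Some precision is lost. More important in principle, the 6-month estimate can be biased if leaving depends on the 3-month level, above all if it does so differently in the two arms. Enlarging the sample for dropout protects power but does nothing about bias.

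The same sentence also offers the 3-month level as a covariate for the final level. That value is measured after randomisation and may already carry part of the effect of the flour, so adjusting for it removes part of what the trial wants to estimate.

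**Working it through.** **1. The plan's own figures.** Two-sided 5%, power 90%, n = 2·SD²·(1.960 + 1.282)²/difference².
- Retinol: difference 34.2 − 29.2 = 5.0; pooled SD = √((10.2² + 9.5²)/2) = 9.86. This gives n = 82 by the normal approximation and 83 by the noncentral t (stated: 83).
- Ferritin: difference 25.2 − 18.01 = 7.19; pooled SD = √((13.8² + 15.3²)/2) = 14.57. This gives n = 87 and 88 (stated: 87).
- Doubling: 2 × 87 = 174, stated as 175 per group.

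The stated numbers reproduce. The planned retinol effect is 5.0/9.86 = 0.51 SD.

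**2. Power on completers.** Assume 20% dropout: 175 × 0.8 = 140 per group, 4 × 0.8 = 3.2 children per bari, design effect 1 + 2.2 × ICC. The dropout rate and the ICC are assumptions.
- ICC 0.1: power 97.0% (retinol), 96.2% (ferritin).
- ICC 0.2: 94.3% and 93.1%.
- ICC 0.3: 90.9% and 89.3%.

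The doubling therefore covers a completer analysis up to 140/87 = 1.61, that is, an ICC of about 0.61/2.2 = 0.28.

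**3. Precision.** Let d be the share lost after the 3-month draw and r the correlation of the 3- and 6-month values given baseline. Then variance(joint)/variance(completers) = 1 − d·r². With equal correlations ρ at all visits, r = ρ/(1 + ρ). With correlation decaying by visit, r = ρ/√(1 + ρ²).

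| Pattern | r | Variance cut, d = 10% | d = 20% |
|---|---|---|---|
| equal, ρ = 0.5 | 0.333 | 1.1% | 2.2% |
| equal, ρ = 0.7 | 0.412 | 1.7% | 3.4% |
| decaying, ρ = 0.7 | 0.573 | 3.3% | 6.6% |

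At d = 20%, with children treated as independent, the joint model is worth 140/0.9778 = 143, 140/0.9661 = 145 or 140/0.9342 = 150 completers per group instead of 140.

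**4. Bias by hand.** Suppose 15% leave in each arm. Control leavers are 0.5 SD low at 3 months, fortified leavers are typical, and the slope of the 6-month on the 3-month value given baseline is 0.6 (all assumed). The completer contrast shifts by 0.15/0.85 × 0.6 × 0.5 = 0.053 SD. That is 0.053 × 9.86 = 0.52 µg/dL, about a tenth of 5.0.

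**5. Bias by simulation.** 400,000 independent children, true 6-month effect 5.0, assumed 3-month effect 2.5, equal correlations. Where leaving depends on the 3-month value, the log-odds change by 1 per SD. Cells give the estimate at 10% / 20% dropout.

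| ρ | Dropout mechanism | t test | ANCOVA on baseline | Joint |
|---|---|---|---|---|
| 0.5 | same in both arms | 4.91 / 4.88 | 4.95 / 4.93 | 5.00 / 5.00 |
| 0.5 | one arm only | 5.47 / 5.80 | 5.23 / 5.42 | 4.99 / 4.99 |
| 0.5 | opposite | 5.87 / 6.73 | 5.44 / 5.91 | 5.00 / 5.03 |
| 0.7 | same in both arms | 4.88 / 4.80 | 4.96 / 4.93 | 5.00 / 4.99 |
| 0.7 | one arm only | 5.69 / 6.25 | 5.22 / 5.39 | 5.01 / 5.01 |
| 0.7 | opposite | 6.27 / 7.38 | 5.40 / 5.75 | 5.01 / 4.99 |

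**6. The 3-month level as covariate.** With equal correlations, adjusting for baseline and the 3-month value leaves 5.0 − ρ/(1 + ρ) × 2.5. That is 5.0 − 0.83 = 4.17 at ρ = 0.5 and 5.0 − 1.03 = 3.97 at ρ = 0.7. The simulation agrees (4.15 to 4.18 and 3.95 to 3.99).

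**The case against.** - **Are the 3-month data thrown away?** A reader might infer this, but the protocol does not support it. It uses them to time the onset of change, to compare the groups at 3 months, and possibly as a covariate. Only later dropouts' 3-month values are unused, and only in the 6-month comparison.
- **Is the trial underpowered?** This too might be inferred. The doubling provides for dropout, and completer power at 20% dropout stays above 90% up to an ICC of 0.2. It falls just short only for ferritin at 0.3.
- **Is the gain large?** A variance cut near 10% at 20% dropout would need r = 0.7. Equal correlations cannot give that, since r then stays below 0.5. A decaying pattern needs an adjacent-visit correlation of about 0.98. Children lost before the 3-month draw add nothing under either method.
- **Is bias likely?** The larger values need dropout that follows the 3-month level differently by arm. Double-blinding and six flour codes make that less likely, and the protocol mentions no return of retinol results to families. It is not excluded. An ANCOVA on baseline already tolerates dropout that depends on arm and baseline.
- **Is this a matter for the analysis plan?** Missing-data rules may well sit in a plan that is not shown, and their absence here is no finding. That does not answer the point, which concerns the tests the protocol names and the covariate it permits.

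**Conclusion.** The point holds in a limited form. The named 6-month comparisons are completer-only although dropout is expected, and a better use of data already collected is available at little cost.

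The precision gain is about 1-3% of variance with equal correlations of 0.5-0.7 and 10-20% dropout after the 3-month draw, and up to about 7% with a decaying correlation of 0.7. Bias from dropout that depends on the 3-month value is about 0.1 of a true 5.0 when both arms behave alike (0.04 to 0.20 in the cases run). When they differ it is 0.22 to 0.91 for the baseline ANCOVA and 0.47 to 2.38 for the t test.

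Dropout rates, correlations, mechanisms and the 3-month effect are all assumptions, because the protocol gives none of them. The precision and bias figures also ignore clustering within baris. The results do not show that the planned analysis will be biased, only that it is open to a bias that the joint model removes when dropout depends on observed values.

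The permitted adjustment for the 3-month level is the more definite fault in that sentence. It lowers the estimate whenever the flour has already raised retinol by 3 months.

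**What to change.** Replace the comparison wording in Data Analysis along these lines:

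- For each marker, fit one repeated-measures mixed model to the 3- and 6-month values. Include the baseline value, arm, visit and arm-by-visit as terms, with within-child correlation and a random effect for bari.
- Include every child with a baseline and at least one later sample.
- Report the arm difference at 6 months as primary and take the 3-month difference from the same model.
- Analyse skewed markers on the log scale. Ferritin is a likely case: the cited 18.01 ± 13.8 µg/L puts two SDs below the mean at 18.01 − 27.6 = −9.6, which is impossible.
- Do not use the 3-month level as a covariate for the treatment effect.
- Keep the 6-month completer ANCOVA, adjusted for baseline only, as a sensitivity analysis.

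The cost is protocol wording and slightly more modelling, with no new visits, blood or data. On the log scale the result is a ratio of geometric means, which the report must explain. The model still requires that dropout depends only on observed values. That is a weaker requirement than the completer tests make, but it cannot be checked from the data.

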**STUDY PROCEDURE:**

- Stage I: Recruitment and training of study personnel and forming the bari list for enrolment
- Stage II: Pretest of measurements, procedures and handling/storage/preparation of flour
- Stage III: Enrolment of participants and baseline data collection and initiation feeding
- Stage IV: Mid-point sampling and data collection
- Stage V: Final sampling and data collection
- Stage VI: Data analysis and reporting

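### The protocol allows the ANCOVA of 6-month levels to adjust for the 3-month level, an on-treatment response, and that version does not estimate the 6-month effect named in the aims

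*Protocol*

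**What the plan says.** The Specific Aims fix the time point. The first aim is the effect "Primarily, on their vitamin A status reflected in serum retinol concentration at 6 months"; the second is the effect "Secondly, on iron status reflected in serum ferritin, TfR and hemoglobin concentration at 6 months".

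The Study Procedure places the start of feeding in the same stage as enrolment and baseline sampling: "Enrolment of participants and baseline data collection and initiation feeding". Research Design and Methods says that each measure "will be determined at the start (0 month), at the mid-point (3 months) and at the end of the trial (6 months"). The 3-month sample is therefore taken after about three months of fortified or unfortified chapattis.

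The protocol itself treats that sample as a response. The Project Summary gives its purpose: "A mid-point blood analysis at 3 months will also be done to measure of the onset of a detectable change". Data Analysis adds: "The same data points will be compared after three and six months of consuming" chapattis.

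The same section names Student's t test, or a non-parametric test such as Mann-Whitney, for continuous variables, and multiple regression for confounding. It ends with an analysis of covariance "comparing the final levels of the outcome variables making allowances for any difference between the initial or 3-month levels". It does not say when the initial level is used and when the 3-month level is used. It does not confine the 3-month version to a secondary question, and it does not say which analysis decides the trial.

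**The concern.** A covariate measured before treatment removes chance imbalance and noise and leaves the treatment effect intact. A value of the same marker measured three months into treatment does something different. Any difference between the arms at that point may already be the effect of fortification, and making allowance for it subtracts part of what the trial is meant to estimate. The coefficient then answers whether children with equal 3-month values differ at month 6. That is not the 6-month effect in the aims, and it is not a comparison of the groups as randomised.

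The two covariates joined by *or* therefore answer different questions, and the text gives no rule for choosing. If fortification acts early and the 3-month-adjusted result were taken as the answer, a real effect could look small or absent.

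**Working it through.** **Inputs from the protocol (Sample Size Estimation).** Retinol 29.2 (SD 10.2) before and 34.2 (SD 9.5) after, so a difference of 5.0 µg/dL; 83 per group for retinol and 87 for ferritin at 5% significance and 90% power; the larger figure doubled to 175 per group for clustering and dropout.

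**Reproducing the plan's figure.** Its formula is n = 2·SD²·factor/WD². The mean of the two variances is (10.2² + 9.5²)/2 = 97.145, so SD = 9.856. The two-sided factor is (1.960 + 1.282)² = 10.507. Then n = 2 × 97.145 × 10.507 / 5² = 81.7, that is 82, or 83 with one added for the t distribution. For ferritin, 2 × 212.265 × 10.507 / 7.19² = 86.3, that is 87. Both stated figures are reproduced, and the sample size is not in dispute.

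**Assumptions, because the protocol gives no figure.** Equal SDs at 3 and 6 months; correlation ρ between the visits of 0.3, 0.5 or 0.7; share f of the 6-month effect already present at month 3 of 0, 0.5 or 1; 83 to 87 effective children per arm, meaning that the doubling just covers clustering and dropout.

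**Formulas.** With the 3-month level as covariate, the group coefficient is d6 − ρ·(SD6/SD3)·d3, here 5 − ρ·5f. The residual SD is 9.856·√(1 − ρ²). The standard error is the residual SD × √[(2/n)(1 + d3²/(4·SD²))]. Power is Φ(estimate/SE − 1.96).

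**One case in full** (f = 1, ρ = 0.5, n = 87). The estimate is 5 − 2.5 = 2.5. The residual SD is 9.856 × √0.75 = 8.536. The SE is 8.536 × √[(2/87)(1 + 25/388.58)] = 1.335. Power is Φ(2.5/1.335 − 1.96) = Φ(−0.09), about 46.5%.

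**Results for the 3-month covariate:**

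| Share of effect at month 3 | ρ | Effect left (µg/dL) | Share left | Power, n = 83 | Power, n = 87 |
|---|---|---|---|---|---|
| none | 0.3 / 0.5 / 0.7 | 5.00 | 100% | 92.9 / 96.5 / 99.6% | 93.9 / 97.2 / 99.7% |
| half | 0.3 | 4.25 | 85% | 82.4% | 84.1% |
| half | 0.5 | 3.75 | 75% | 80.2% | 82.0% |
| half | 0.7 | 3.25 | 65% | 83.9% | 85.6% |
| all | 0.3 | 3.50 | 70% | 64.2% | 66.3% |
| all | 0.5 | 2.50 | 50% | 44.8% | 46.5% |
| all | 0.7 | 1.50 | 30% | 26.5% | 27.5% |

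With the initial level as covariate and the same ρ, the effect stays at 5.0 whatever the value of f, and power is that of the first row.

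**Check by simulation** (200,000 per arm, equal correlation ρ among the three visits). Adjusting for the initial level gave 4.99 to 5.04. Adjusting for the 3-month level gave 3.51, 2.52 and 1.49 with the full effect at month 3, and 4.29, 3.77 and 3.27 with half, in line with the formula. Entering both levels does not cure the problem: 3.87, 3.33 and 2.94 with the full effect, and 4.47, 4.18 and 4.00 with half.

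**The case against.** The strongest reply is that the ANCOVA is not named as the deciding test. Data Analysis first plans between-group comparisons at three and six months by t test or a rank test, and adjusting for the 3-month level does not touch those. This stands. A reader might infer that the trial's main result is biased, or that effective fortification will be declared ineffective. The document does not support that, because it never makes the 3-month-adjusted result decisive. Equally, it does not say that another result is, so the flaw remains.

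The sentence may also describe two analyses: month 6 given the initial level, and month 6 given month 3, the second being a fair secondary question about continued change. That is possible, but the text does not say so, and it covers final levels of the outcome variables in general. The donor's review appended to the protocol asks that initial levels be controlled for. That suggests that baseline adjustment was the core intent, but it is an inference.

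A reader might further infer that the analyst will choose the covariate after seeing the results. The protocol leaves the choice open, but an analysis plan not shown here could settle it, and the flour is masked behind six letter codes. Nor does the sentence state a rule of adjusting only if the baselines differ; allowing for differences is ordinary language for ANCOVA.

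On size, the lowest powers need the whole effect to be present by month 3 together with a high correlation. The borrowed 5 µg/dL was seen after one year of fortified sugar, so a complete effect at three months is the unfavourable end of the range. It would also tend to show in the separately planned 3-month comparison. This stands too, and is why the full range is given.

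**Conclusion.** The point holds as a defect in a stated analysis rule. One of the two permitted covariates is affected by treatment, and the resulting coefficient is not the 6-month effect in the Specific Aims. The direction of the bias is towards zero when the 3- and 6-month effects have the same sign and the visits are positively correlated. It vanishes if there is no effect at month 3 or no correlation.

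The size cannot be fixed from the protocol. Under the assumptions listed, the loss runs from nothing to 70% of the planned difference. Power under the 3-month adjustment runs from about 27% to the level obtained with the initial level as covariate. The practical harm depends on whether the 3-month-adjusted result is used for the conclusion, since the unadjusted 6-month comparison is sound in this respect.

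**What to change.** Delete the 3-month option from the ANCOVA sentence. Suitable wording: *The 6-month level of each outcome will be compared between groups by analysis of covariance with the child's initial level of that outcome as covariate.*

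Analyse the 3-month level as an outcome in its own right, adjusted for the initial level; this serves its stated purpose of showing when a change begins. A single repeated-measures model with the 3- and 6-month values both as outcomes and the initial level as covariate would also do, but is optional. If a month 3-to-6 analysis conditional on the 3-month level is wanted, label it exploratory and state that it does not estimate the total effect of fortification.

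The cost is one or two sentences of analysis text. No sample, visit or assay changes.
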